7.3.1 Randomisation System Failure

In the event of a randomisation system failure, the centre should contact the coordinating team at the CTRC (Monday to Friday between 9:00 to 17:00 excluding bank holidays) to inform them of the problem. Out-of-hours the centre should contact the Chief Investigator or his delegates, on [name].

7.4 Blinding to Allocations

BESS will use an established strategy of a sham-procedure to blind as many research and usual care staff as possible to the nature of the intervention. This sham procedure was used in the development of surfactant as a therapy for surfactant deficiency of prematurity (6,19).

The participants, CTRC staff (excluding statistical team members as appropriate), and all members of the site research teams (excluding agreed randomising staff member, the administrator of the intervention and the dosage witness) will be blinded to treatment allocations. Occasional transient adverse effects associated with surfactant administration and back-tracking of surfactant up the endotracheal tube, plus the more frequently observed positive effects of rapid improvement in gas exchange immediately following surfactant administration, may result in some blinded care givers being able to infer that a participant has been allocated to the surfactant arm of the trial. The randomising person, person drawing up the surfactant or air placebo and a second person checking the dose will be unblinded. Due to the transient effects and back-tracking it is likely that the Usual Care Nurse (UCN) will become unblinded, and we therefore recommend that if possible the UCN draws up the surfactant or acts as the witness to the drawing up, to minimise the number of people unblinded. Please see figure 2 for an intervention flowchart showing which staff/steps are blinded and unblinded.

Staff who are unblinded due to their involvement or believe themselves to have become unblinded for any reason are strongly discouraged from discussing this with other members of the team, unless the effect noted is causing an adverse event that requires action. Any staff member who believes themselves to have become unblinded must excuse themselves from any decision making regarding the weaning and extubation of the infant. The need to maintain blinding will be emphasised during all Site Training Visits.

IRAS 220853 Page **33** of **87**

8 PARTICIPANT TIME LINE, ASSESSMENTS AND PROCEDURES

8.1 Administration of Intervention

The first trial intervention must be administered within 2 hours of randomisation with subsequent doses (if required) at 12 and 24 hours post randomisation. A grace period of one hour either side of the anticipated administration time is permitted.

- Randomisation; T0
- First intervention must be given within two hours; between T0 and T2
- Second intervention should be given 12 hours after randomisation; at T12 (+/- 1 hour)
- Third intervention should be given 24 hours after randomisation; at T24 (+/- 1 hour)

8.1.1 Immediately prior to administration

A limited physical examination, with minimal handling, must be undertaken in the two hours prior to each administration of the trial intervention (as per Section 8.5.1).

Prior to intervention and in a drug room away from usual staff, the study respiratory physiotherapist, research nurse or other delegated, unblinded staff member will:

- Draw up a dose of poractant alfa or an equal volume of air as placebo according to the random allocation into a syringe
- Ensure a second person is present to witness this process and check the dose volume
- Cover the syringe with an opaque paper shield to maintain blinding of other staff and parents
- Take the syringe to the bedside, along with syringes of sterile 0.9% sodium chloride for tracheal toilet and the BAL sampling set.

Infants in both the treatment and placebo arms of the trial will have 0.9% sodium chloride "normal saline" tracheal toilet and 0.9% sodium chloride BAL immediately prior to administration of the intervention. Both can cause immediate transient desaturation, need for increased sedation but also and more often rapid improvement in gas exchange when obstructing secretions are removed. Tracheal toilet and BAL can also lead to creamy white secretions appearing in the endotracheal tube, and this will be observed in both treatment and placebo groups.

Staff should remind parents, if present, of the purpose of the imminent study procedure and give them the opportunity to remain or leave as they choose. The usual care nurse will remain to care for the participant and assist as required.

Tracheal toilet is usually required for babies with bronchiolitis and will be done as recommended in the SPC before administration of poractant alfa. BAL sampling with 0.9% sodium chloride (2x1mL/kg) will be done if scheduled (section 8.2). Both tracheal toilet and BAL sampling is done by catheter access to the trachea; either via the endotracheal suction port without disconnecting the

IRAS 220853 Page **34** of **87**

infant from the ventilator or by disconnecting the infant from the ventilator and performing hand bagging while a side-port with one-way valve are utilised for the toilet and BAL.

The use of muscle relaxant prior to tracheal toilet, BAL and or administration of the intervention is at clinical discretion.

8.1.2 Administration of allocated intervention

The intervention will be given per either method described in the SPC; either keeping the infant connected to the ventilator or momentarily disconnecting and performing hand-bagging (at the attending Respiratory Physiotherapist's decision based on patient status).

- Connect the syringe containing the surfactant or air-placebo to a suitable catheter (size 5F);
- Pass the catheter through the suction or side port into the endotracheal tube and advance the catheter, aiming to have the tip of the catheter placed just beyond the tip of the endotracheal tube
- Deliver the intervention (surfactant or air-placebo) slowly as a single bolus (recommended over 0.5-3 minutes) directly into the lower trachea
- The intervention (surfactant or air-placebo) will disperse through mechanical ventilation cycles into the peripheral lung tissue where the excipient (sterile buffered 0.9% sodium chloride) is absorbed in the alveoli and the surfactant phospholipid is deposited.

8.1.3 Post administration of allocated intervention

All participants must be given a limited physical examination, with minimal handling, in the interval between one hour and two hours after the administration of each intervention dose (see section 8.5.1).

8.1.4 Weaning and extubation by protocol

The unblinded staff involved in the administration of the BESS intervention (study respiratory physiotherapist or nurse practitioner or other qualified person and one usual care PICU nurse) and parents who may be observing, will not be involved in decisions to wean respiratory support provided by mechanical ventilation and will not be involved in decisions to extubate.

We will wean respiratory support provided by MV and extubate according to a standardised protocol that will form part of the site-specific training packages.

Readiness for a spontaneous breathing test (SBT) will be identified by the patient meeting specified physiological targets of gas exchange at a given level of ventilation and/or the treating clinician believes the child to be ready for SBT.

The time at which a child is deemed ready for SBT **must** be recorded in their notes/electronic health record. The time that a child is extubated **must** be recorded in their notes/electronic health record.

IRAS 220853 Page **35** of **87**

8.2 Participant follow-up

Clinical follow-up (daily data collection) will take place for the period of time between randomisation and the discharge from hospital of the participant.

All non-serious adverse events will be collected until 24 hours after the participant receives their final trial intervention; please note that this may not be their third dose if less than 3 doses are required before the participant meets the criteria to be ready for weaning (see section 10 for full safety reporting information).

Non-serious adverse events occurring after 24 hours post-final intervention but before 90 days post-randomisation/discharge home/death should be reported if the local Investigator believes that they may be related to the intervention.

Although active monitoring for adverse events and adverse reactions will cease at 24 hours post final intervention and 90 days post randomisation / discharge home / death respectively, any which the site research team become aware of after these time-points which are assessed as serious (i.e. Serious Adverse Events or Serious Adverse Reactions) should be reported to the CTRC. Routinely collected audit data regarding participant care will be collected from PICANet until 90 days post randomisation.

Parent reported outcomes will be collected via the LRSQ at 6 and 12 months post randomisation for participants recruited in seasons 1 and 2, and at 6 months only for participants recruited in season 3.

The end of follow-up definition for each participant will therefore be 12 months post randomisation for participants in season 1 and 2, or 6 months post randomisation for participants in season 3.

IRAS 220853 Page **36** of **87**

8.3 Schedule for Intervention & Follow-up

Table 2: Schedule for intervention and follow-up

Procedures	Staff	Consent & randomisation	prior to first intervention	1-2hr,post first intervention	6hr	12hr, prior to second intervention	1-2hr post second intervention	24hr, prior to third intervention	1-2hr post third intervention	36hr	48hr	Daily if MV	p06	6m	12m
Prescribe	PI/Dr	Χ													
Invitation to participate in WP-B (parental experience sub-study)	PI/Dr/RN	X*													
+Invitation to participate in WP-C (surfactant metabolism sub-study)	PI/Dr/RN	X*													
*Blood Gas sample (capillary or arterial)	N/RN		Х		Х	Х		Х		Х	Х	Х			
CRF completion (patient data collection)	N/RN		Х		Х	Х		Х		Х	Х	Х			
Limited physical examination	N/RN/Dr		Χ	Χ		Х	Х	Х	Х						
*BAL	RP		Х			X+		Х		X+		Х			
Administration of trial intervention	RP		Х			Х		Х							
+IV D-Choline	N/RN		X+												
+Blood Sample (venous or arterial)	N/RN		X+			X+		X+		X+	X+				
Safety monitoring and reporting	RN/RP/PI\$		Х		Х	X		Х		Х	Χ	Χ			
LRSQ	RN													Χ	X*
Mortality and re- admission	RN												Х		

 $RN = Research \ Nurse, \ RP = Study \ respiratory \ physiotherapist or nurse practitioner or any other qualified person not involved in decision to wean or extubate, <math>PI = Local \ Principal \ Investigator \ or \ delegate, \ N = Nurse \ (usual \ care), \ Dr = Research \ Nurse \ (usual \ care)$ licensed medical practitioner.

IRAS 220853 Page 37 of 87

 $^{^{\}mathbf{x}}$ Before each trial intervention

⁺ Only at Liverpool & Southampton and with specific consent (see section 12.2) * Seasons 1 & 2 only

^{\$} Although all delegated staff are responsible for identifying and reporting adverse events, decisions regarding causality and seriousness, and sign-off of serious adverse event reports can only be undertaken by a licensed medical practitioner.

[figure not shown]

Figure 2: BESS Intervention Schedule

IRAS 220853 Page **38** of **87**

8.4 Procedures for assessing Efficacy

8.4.1 Efficacy Assessment 1

Efficacy will be assessed by group-wise comparison of the primary outcome measure group "Duration of MV after randomisation" by intention to treat. This is defined as time from randomisation to final extubation in hours, including any time off MV where the infant requires reintubation for a further period of MV. Time of randomisation and intervention will be recorded in the patients' notes and CRFs. MV ceases at extubation, an event when the endotracheal tube (breathing tube) is removed and the infant is allowed to breathe without invasive mechanical support. Extubation is an important discrete event in a patient's care pathway, is routinely recorded in the notes and PICANet audit.

8.4.2 Efficacy Assessment 2

The Ventilation Index (VI), Oxygenation Index (OI), Oxygenation Saturation Index (OSI) and SF ratio are secondary outcomes of efficacy derived from blood gas results (capillary blood gas sampling times as per Table 2 Schedule for intervention and follow-up), ventilator settings, and non-invasive monitoring. These data are captured through existing intensive care automated monitoring process or regular manual entry on large format (broad-sheet) bed-charts. This data will be transcribed by the research nurse to the CRF.

Mechanical Ventilation parameters to allow calculation of VI, OI, OSI and SF ratio must be recorded at the corresponding time when Blood Gas samples are scheduled to be taken for research or taken for routine purposes.

Mechanical Ventilation parameters are recorded regularly for ventilated patients as part of standard care. BESS does not require site teams to take any additional readings of these parameters for study purposes, but **all blood gas and ventilator readings** taken as part of standard care must be transcribed into the CRF to allow for calculation of these ratios over time.

After extubation, all inhaled Oxygen and peripheral oxygen saturation parameters recorded as part of standard care must be transcribed into the CRF to allow for calculation of this ratio over time. Blood gas indices and ratio definitions are as follows:

- VI = (PaCO₂ × (PIP-PEEP) × respiratory rate)/1,000
- OI = $(MAP \times FiO_2 \times 100)/PaO_2$
- OSI = $(MAP \times FiO_2 \times 100)/SpO_2$
- SF = SpO₂/FiO₂

MAP = mean airway pressure

PaCO₂ = partial pressure of arterial carbon dioxide

 FiO_2 = Fraction of air inspired that is oxygen

 PaO_2 = partial pressure of arterial of oxygen

SpO₂= peripheral oxygen saturation

The time that physiological criteria are met that indicate suitability to test readiness for extubation by spontaneous breathing and/or the treating clinician believes the child to be ready for SBT will be recorded in the patient medical records and CRF.

All-cause mortality at 90 days after intervention will be established via a local enquiry against the hospital electronic health record.

IRAS 220853 Page **39** of **87**

8.5 Procedures for Assessing Safety

Safety will be assessed by:

- The Principal Investigator (PI) or delegated research staff actively monitoring and reporting all adverse events from randomisation until 24 hours after the participant's last administration of poractant alfa (see section 10 for adverse event reporting).
- Limited physical examination that includes the recording of vital signs before and after each study intervention
- Routinely collected patient care data downloaded from the PICANet audit on a regular basis by each site and transferred to the CTRC
- Mortality and readmission data collected by each site at 90 days post randomisation

Participants will be actively monitored and any adverse events identified must be reported to the CTRC, whether identified from trial assessments or standard care (e.g. identified during standard daily examinations). Non-related events will be reported from randomisation to 24 hours after the participant's last administration of poractant alfa or placebo for. Adverse events occurring after this time point until 90 days post randomisation / discharge home / death will be reported if felt to be related to the intervention. Any serious events or reactions (SAEs/SARs) should be reported to CTRC regardless of the timeframe.

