Primary Objective To determine the efficacy of endotracheal surfactant in reducing total duration of MV by 18 hours or more, by random blind allocation of infants to receive either up to 3 doses of poractant alfa or up to 3 doses of air-placebo in an identical administration procedure.	Total duration of MV (hours) from randomisation to final extubation, including any time off MV due to failed extubation.	N/A
Secondary Objective 1 To describe the impact of intervention on infants' long term respiratory symptoms	The score (value) of patient reported outcome measure of respiratory systems in the "Liverpool Respiratory Symptom Questionnaire" (LRSQ)	LRSQ at 6 months and 12 months post randomisation
Secondary Objective 2 To describe secondary outcomes of efficacy including physiological	Time from randomisation to meeting study criteria for readiness for Spontaneous Breathing Test	N/A
indices and duration of other modes of respiratory support	Number of trial interventions given Change over time from baseline of Ventilation Index (VI), Oxygenation Index (OI) and Oxygenation Saturation Index (OSI) while mechanically ventilated, & SpO ₂ /FiO ₂ (SF) ratio Duration of oxygen supplementation Use of steroids to assist extubation	N/A Capillary blood gas sampling immediately prior to intervention and then at 6, 12, 24, 36 and 48hrs while still on MV; to continue daily after 48hrs if still on MV. N/A N/A

IRAS 220853 Page **22** of **87**

	Duration of post-extubation non-invasive respiratory support Duration of stay on PICU and in hospital	N/A N/A
Secondary Objective 3 To assess the safety of the intervention for infants with life-threatening bronchiolitis	Failure to administer the intervention due to any adverse event during preparatory processes (tracheal toilet or BAL)	Randomisation to 24 hours after final trial intervention
	Failure to complete administration of the intervention due to any adverse event during administration of the intervention (regardless of which arm of allocation)	Randomisation to 24 hours after final trial intervention
	Incidents of 'air leak' (pneumothorax and pneumomediastinum) occurring before discharge from PICU	Randomisation to discharge from PICU
	Other adverse events and serious adverse events associated with the intervention	Randomisation to 24 hours after final trial intervention
	Any need to replace the endotracheal tube	Randomisation to successful extubation

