10.7 Time Period for Safety Reporting

Investigators and delegated members of the local research teams will report to CTRC on the appropriate CRFs (see section 10.8):

- all adverse events from randomisation until 24 hours after their final intervention (whether poractant alfa or placebo);
- all adverse reactions from randomisation until 90 days post-randomisation or hospital discharge (whichever is sooner).

Following these periods, site staff are not required to report any non-serious events, however any serious events (SAEs/SARs/SUSARs) which they become aware of must be reported to CTRC.

[figure not shown]
Upon becoming aware of a serious adverse event (SAE/SAR/SUSAR), the Investigator or other delegated member of the team **must** report this to the CTRC **within 24 hours**.

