#### 20.2. Presentation of the data

All AEs reported by the clinical investigator will be presented, with separate tables for serious and non-serious events. Both the number of events and the number of patients experiencing each event will be provided. A third table will be presented grouping non-serious AEs by severity; participants will be counted in the most severe category experienced if they experienced more than one. Similarly, a fourth table will be presented grouping non-serious ARs by causality (where the relationship to intervention is recorded as possibly, probably or almost certainly) and participants will be counted in the highest relationship category experienced if they experienced more than one.

The above tables for serious and non-serious events will be repeated but will be further grouped by whether or not the patient received muscle relaxant prior to the administration of the intervention. Serious adverse reactions will be presented as line listings, detailing the description, seriousness, severity, expectedness, relationship to intervention and outcome.

Relationship to study drug will be assessed first assuming the participant is in the intervention arm, then assuming they are in the control arm, so as to avoid unnecessary unblinding. However, for the classification of causality only the relationship to the intervention received will be reported.

For all AE descriptions, MedDRA classifications will be used. Events will be reported using the preferred term, categorised by system organ class. Results will be presented descriptively; no formal statistical testing will be undertaken for interim reports.

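### SAP 20.2 tabulates all reported adverse events with no time window, so each table mixes a complete early period with a selectively reported later one

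*Protocol*

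**What the plan says.** **Collection.** Protocol 8.2 sets the first rule: "All non-serious adverse events will be collected until 24 hours after the participant receives their final trial intervention". It adds a caution about where that window ends: "please note that this may not be their third dose if less than 3 doses are required". For events after that point, protocol 8.5 says they "will be reported if felt to be related to the intervention", up to 90 days, discharge home or death. SAP 8.8 repeats this relatedness condition for non-serious events. Protocol 10.7 words the end of the related-event period differently: "all adverse reactions from randomisation until 90 days post-randomisation or hospital discharge (whichever is sooner").

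For serious events, protocol 8.5 says "Any serious events or reactions (SAEs/SARs) should be reported to CTRC regardless of the timeframe". Protocol 10.7 makes clear that, once the active periods are over, this means "any serious events (SAEs/SARs/SUSARs) which they become aware of must be reported to CTRC". No end date is given.

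**Outcome period.** Protocol Table 1 (section 3.6.2) lists other AEs and SAEs linked to the intervention as a safety outcome, with the period "Randomisation to 24 hours after final trial intervention".

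**Presentation.** SAP 20.2 says: "All AEs reported by the clinical investigator will be presented, with separate tables for serious and non-serious events". It asks for counts of events and of patients, by MedDRA preferred term within system organ class. It states no cut-off, no split by period and no person-time. SAP 9.2 does not list the Table 1 AE/SAE outcome, and it is not among the six safety outcomes in SAP 17.5.

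**The concern.** A reader of an AE table assumes that every event in it had the same chance of being recorded, over a period that can be named. Neither holds for a table built as SAP 20.2 describes. The early part is complete. The late non-serious part contains only events that someone thought were related. The late serious part contains whatever reached the site.

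Relatedness judgements may differ by arm. Protocol 7.4 expects some blinded caregivers to infer that an infant received surfactant. A filter that passes more events in one arm adds events to that arm's total without any true difference in harm. For serious events, later background illness added to both arms makes a real excess around dosing look proportionally smaller.

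SAP section 5 says the analysis report will support EudraCT posting and the primary publications, so these tables will be read even though they carry no formal comparison.

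**Working it through.** The plan states no figure on this point, and the sample size does not bear on it. The check sets the rules side by side and then does arithmetic on the dose schedule. All event rates below are assumptions.

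**1. What reaches each table** (protocol 8.2, 8.5, 10.7; SAP 8.8, 20.2)

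| Onset | Non-serious table | Serious table |
|---|---|---|
| Randomisation to 24 h after last intervention | all, actively sought | all, actively sought |
| Then to 90 days, discharge or death | only if judged related | related or not; depends on site awareness |
| Later | none required | any the site learns of, no end date |

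No relatedness filter applies to reporting late serious events. Protocol 8.2 does continue active monitoring for adverse reactions longer than for adverse events in general, so awareness may be better for related ones.

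**2. Length of the all-event window.** Protocol 8.1 places the doses at 0–2 h, 12 ± 1 h and 24 ± 1 h after randomisation. Window = time of last dose + 24 h.

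- One dose: 0–2 + 24 = 24–26 h
- Two doses: 11–13 + 24 = 35–37 h
- Three doses: 23–25 + 24 = 47–49 h

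Ninety days is 90 × 24 = 2160 h. The complete window is therefore 24/2160 = 1.1% to 49/2160 = 2.3% of it. Between one and three doses the window varies about twofold (47/26 = 1.8 to 49/24 = 2.0).

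**3. Effect of dose number inside that window.** SAP 17.4.3 compares the number of interventions between arms, so window length may differ by arm. Take a nominal window of 12 × doses + 12 h and an equal hourly event rate in both arms.

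- Mean doses 2.0 v 2.0: 36/36 = 1.00
- 2.0 v 2.4: 36/40.8 = 0.88
- 2.0 v 2.8: 36/45.6 = 0.79

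**4. Effect of the relatedness filter.** Assume one early event per infant and L late non-serious events per infant, with the same true rates in both arms. Let a proportion p of late events be judged related. Count per infant = 1 + L × p.

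| p, surfactant v placebo | L = 1 | L = 3 |
|---|---|---|
| 5% v 5% | 1.05/1.05 = 1.00 | 1.15/1.15 = 1.00 |
| 10% v 5% | 1.10/1.05 = 1.05 | 1.30/1.15 = 1.13 |
| 20% v 5% | 1.20/1.05 = 1.14 | 1.60/1.15 = 1.39 |

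**5. Effect of late serious events.** Assume 20 v 10 SAEs in the window, a ratio of 2.0. If sites also hear of 20 later SAEs in each arm, the totals are 40 v 30, a ratio of 1.33. The absolute difference stays at 10.

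**6. Comparison with the other safety outcomes.** SAP 17.5 states a period for each of its six outcomes. The AE and SAE tables in SAP 20.2 have none, although protocol Table 1 supplies one.

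**The case against.** The strongest reply is that little depends on these tables. They are descriptive, and no formal test of them is specified (the explicit no-testing sentence in SAP 20.2 is worded for interim reports). Failed administration, air leak, tube replacement, readmission, PICU death and 90-day mortality each have their own period and between-arm comparison in SAP 17.5. Reporting by preferred term keeps typical peri-dose events largely on separate rows from later illness. In the serious-event illustration only a ratio of totals moves, and the SAP plans no such ratio. All of this stands, and it limits the point.

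There are also safeguards on causality. Protocol 10.9.1 has it evaluated as for poractant alfa unless the infant is unblinded. SAP 20.2 has relatedness assessed under each arm in turn, although only the relationship to the intervention received is then reported. These measures reduce differential judgement but do not remove the filter.

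The protocol to hand is version 2.0, while the SAP refers to versions 3.0 and 6.0, so Table 1 may have changed. The mixing of non-serious events does not depend on that, because SAP 8.8 itself contains the relatedness condition. Table 1 is also limited to events linked to the intervention, so neither the SAP's all-AE tables nor an all-event table for the early window matches it exactly.

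A reader might infer that everything is pooled into one count per arm. It is not: serious and non-serious events are separate, with further tables by severity, causality and muscle-relaxant use. A reader might also infer that late SAEs are filtered on causality, but unrelated ones are reportable too. Nor does every readmission become an SAE. Later reports depend on awareness, and protocol 10.1 excludes hospitalisation for a pre-existing condition that has not worsened.

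**Conclusion.** The point holds as a gap in SAP 20.2. Followed as written, each table adds a complete window of about 24 to 49 hours to a later period collected under a weaker rule: judged relatedness for non-serious events, site awareness for serious ones. The protocol does define a risk period for this outcome; the SAP does not use it.

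The distortion cannot be sized from the documents. On the assumed rates above, a pooled non-serious ratio with no true difference runs from 1.00 (equal judgement) to 1.39, and a serious-event ratio of 2.0 falls to 1.33. These figures show direction only. The documents do not support a claim that the tables will be biased in a particular direction, or that the trial's main safety comparisons are affected. Because the consequence is confined to descriptive tables and the remedy is cheap, this is a change that should be made rather than one on which the trial's conclusions depend.

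**What to change.** In SAP 20.2, split the AE and SAE tables by onset period and do not add the periods together for the between-arm display.

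1. Randomisation to 24 hours after the final intervention, all events. This is the between-arm display. Because the window depends on doses received, show the number of doses or person-time alongside it, or add a table to 24 hours after the first dose, the longest window in which every dosed infant is under the all-event rule.
2. Later non-serious events, in a separate table labelled as judged related by the investigator.
3. Later SAEs, in a separate table or listing labelled as passively reported.

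Complete listings of all SAEs can stay for regulatory posting.

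Three wordings also need reconciling:
- the end of the related-event period in protocol 8.2 and 8.5 against 10.7;
- Table 1's restriction to events linked to the intervention against the SAP's all-AE tables;
- the bullet in protocol 8.5 that ends active monitoring after the last poractant alfa dose, against the text below it that also names placebo.

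The cost is SAP wording, a derived period flag and more tables. Protocol 8.4.1 says intervention times are recorded. Onset date is documented for the SAE form (protocol 10.8.3); confirm that the AE form records it too.
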